**Table 6 Study Schedule: Expansion of continued supply phase (Groups 1 and 2)**

Visit	Screening	2	3	4	5	6	7	8	9	10 i	Final Follow-up (30 days after Treatment Discontinuation)	Treatment Discontinuation
Day a	-28 to -1	1	8	15	29	57 (+/- 2)	85 (+/- 2)	113 (+/- 2)	141 (+/- 2)	169 (+/- 2)		
Informed consent	X											
Demographics	X											
Medical and surgical history	X											
Inclusion/exclusion criteria	X											
Pregnancy test j	X											
Randomisation		X										
Physical exam	X	X a			X	X	X	X	X	X	X	X
Vital signs, body weight b	X	X a			X	X	X	X	X	X	X	X
ECOG performance status	X	X a			X	X	X	X	X	X	X	X
ECG c	X	X			X	X					X	
Haematology / clinical chemistry	X	X a			X	X	X	X	X	X	X	X
Urinalysis	X	X a			X	X	X	X	X	X	X	X
Adverse Events d	X	X			X	X	X	X	X	X	X	X

**Table 6 Study Schedule: Expansion of continued supply phase (Groups 1 and 2)**

Visit	Screening	2	3	4	5	6	7	8	9	10 i	Final Follow-up (30 days after Treatment Discontinuation)	Treatment Discontinuation
Day a	-28 to -1	1	8	15	29	57 (+/- 2)	85 (+/- 2)	113 (+/- 2)	141 (+/- 2)	169 (+/- 2)		
Concomitant medications	X	X			X	X	X	X	X	X	X	X
AZD2281 dispensed/returned		X	Group 2	Group 2	X	X	X	X	X	X	X	X
Pharmacokinetics			X e, f	X e, f	Group 1 e							
Tumour Assessment h	Group 1					Group 1 g		Group 1 g		Group 1 g		
Blood sampling for CA-125	Group 1	Group 1 k				Group 1 k		Group 1 k		Group 1 k		

a If assessed within 7 days before enrolment and meets the stated eligibility criteria (if applicable), it need not be repeated on Day 1 of cycle 1 unless Investigator believes that it is likely to have changed significantly.

[figure not shown]
b Vital signs include BP, pulse and body temperature will be measured at least monthly for a minimum of 6 cycles of treatment, at least every 2 months thereafter, and on final follow up visit until study completion or treatment discontinuation. Patient is to be in the supine position for BP and pulse. Body weight will be measured at screening, Day 1 and on the Final Follow-up Visit. Height will be measured at screening only.

c ECGs are required within 7 days prior to start of study medication, at least monthly for the first three months and at 30-day follow-up and when clinically indicated, see Section 7.3.5.2. ECG should be performed once the patient has been in the supine position for at least 5 minutes in each case. ECG Traces will be stored with the CRFs and collected by the monitor.

d AEs must be collected from the time of informed consent, throughout the treatment period and up to and including the follow-up period. All ongoing AEs must be monitored until resolution unless, in the Investigator’s opinion, the condition is unlikely to resolve due to the patient’s underlying disease. After discontinuation from treatment, patients must be followed up for all existing and new AEs for 30 calendar days (if SAEs, they must be reported to AstraZeneca within 24 hours) and followed until resolution unless, in the opinion of the Investigator, the condition is unlikely to resolve due to the patient’s underlying disease.

[figure not shown]

- c For the 20 additional gBRCA patients that are recruited to Group 1, blood samples will be collected immediately prior to the first dose of the day on day 8, day 15 and day 29 and post the first dose of the day on day 29 between 0 - 0.5 hours, 0.5 to 1.5 hours, 1.5 - 3 hours, 3 - 6 hours and 6 - 12 hours.
- f For the 6 additional patients that are recruited to Group 2, PK sampling will occur on both day 8 and day 15 at the following timepoints within each day: Pre-dose, 0.25, 0.5, 1, 1.5, 2, 3, 4, 6, 8, 10, 12 hours after morning dosing.
- g For the additional 20 gBRCA patients recruited to the Continued Supply Expansion Phase and assigned to Group 1, follow-up tumour assessments will be performed every 8 weeks (+/-1 week) until disease progression. Any other sites at which new disease is suspected should also be appropriately imaged. If scans are performed outside of scheduled visit  $\pm$  1 week window interval and the patient has not progressed, every attempt should be made to perform the subsequent scans at their scheduled time points. Patients must be followed until progression regardless of whether study treatment is discontinued or delayed and/or protocol violation. A repeat scan is needed at the next scheduled tumour assessment (at least  $\geq$  4 weeks) for confirmation of a PR or CR by RECIST. Radiological examinations performed in the conduct of the study should be retained at site as source data and may be collected by the sponsor if required.
- h For the additional 20 gBRCA patients recruited to the Continued Supply Expansion Phase and assigned to Group 1, the imaging modalities used for RECIST assessment will be CT or MRI scans of chest, abdomen and pelvis for breast cancer and abdomen and pelvis for ovarian cancer with other regions as clinically indicated for the assessment of disease. An historical scan meeting the RECIST criteria as defined in [Appendix F](#) can be used for baseline assessment, but this must be performed no more than 28 days before the first dose of study medication.
- i After the follow up visit at the end of the 6th cycle of treatment (Visit 10), this visit should be repeated every 8 weeks until either the patient discontinues study treatment or the study is completed (see Section [10.5](#)).
- j Pre-menopausal women of child-bearing potential must have a negative urine or serum pregnancy test within 7 days prior to Day 1 of Treatment Period 1. In the event of suspected pregnancy during the study, the test should be repeated and, if positive, the patient discontinued from study treatment immediately.
- k Blood samples for CA-125 analysis should be taken prior to the morning dose of study medication.

**Table 7 Study Schedule: Dose escalation phase of the continued supply expansion (Groups 3-8)**

Visit	Screening	2	3	4	5	6	7	8	9	10	11	12	13 j	Treatment Discontinuation	Final Follow-up (30 days after Treatment Discontinuation)
Day	-28 to -1	1	8	15	22	29	43 (+/- 2)	57 (+/- 2)	71 (+/- 2)	85 (+/- 2)	113 (+/- 2)	141 (+/- 2)	169 (+/- 2)		
Informed consent	X														
Demographics	X														
Medical and surgical history	X														
Inclusion/exclusion criteria	X														
Pregnancy test k	X	X													
Randomisation		X													
Physical exam q	X	X a	X	X	X	X		X		X	X	X	X	X	X
Vital signs, body weight b,q	X	X a	X	X	X	X		X		X	X	X	X	X	X
ECOG performance status q	X	X a	X	X	X	X		X		X	X	X	X	X	X
ECG c,q	X	X a				X		X							X
Haematology / clinical chemistry	X	X a	X	X	X	X	Group 3-5 m	X	Group 3-5 m	X	X	X	X	X	X
Urinalysis r	X	X a	X	X	X	X		X		X	X	X	X	X	X

**Table 7 Study Schedule: Dose escalation phase of the continued supply expansion (Groups 3-8)**

Visit	Screening	2	3	4	5	6	7	8	9	10	11	12	13 j	Treatment Discontinuation	Final Follow-up (30 days after Treatment Discontinuation)
Day	-28 to -1	1	8	15	22	29	43 (+/- 2)	57 (+/- 2)	71 (+/- 2)	85 (+/- 2)	113 (+/- 2)	141 (+/- 2)	169 (+/- 2)		
Adverse Events d, p	X	X	X	X	X	X		X		X	X	X	X	X	X
Concomitant medications	X	X	X	X	X	X		X		X	X	X	X	X	X
AZD2281 dispensed/returned		X				X		X		X	X	X	X	X	X
Pharmacokinetics		X c	X c	X c		X f, g		Group 6 & 7 n							
Pharmacokinetics (Group 8 only)		Xo	Xe					Xo							
Archival tumour sample for biomarker analysis	Group 6, 7 & 8 n														
Tumour Assessment i	Group 6, 7 & 8							Group 6, 7 & 8 h		Group 6, 7 & 8 h		Group 6 & 7 h			
Blood sampling for CA-125	Group 6, 7 & 8	Group 6, 7 & 8 l						Group 6, 7 & 8 l		Group 6, 7 & 8 l		Group 6 & 7 l			

a If assessed within 7 days before enrolment and meets the stated eligibility criteria (if applicable), it need not be repeated on Day 1 of cycle 1 unless Investigator believes that it is likely to have changed significantly.

- b Vital signs include BP, pulse and body temperature will be measured at least monthly for a minimum of 6 cycles of treatment, at least every 2 months thereafter, and on final follow up visit until study completion or treatment discontinuation. Patient is to be in the supine position for BP and pulse. Body weight will be measured at screening, Day 1 and on the Final Follow-up Visit. Height will be measured at screening only.
- c ECGs are required within 7 days prior to start of study medication, Day 29, Day 57 and at 30-day follow-up and when clinically indicated, see Section 7.3.5.2. ECG should be performed once the patient has been in the supine position for at least 5 minutes in each case. ECG Traces will be stored with the CRFs and collected by the monitor.
- d AEs must be collected from the time of informed consent, throughout the treatment period and up to and including the follow-up period. All ongoing AEs must be monitored until resolution unless, in the Investigator's opinion, the condition is unlikely to resolve due to the patient's underlying disease. After discontinuation from treatment, patients must be followed up for all existing and new AEs for 30 calendar days (if SAEs, they must be reported to AstraZeneca within 24 hours) and followed until resolution unless, in the opinion of the Investigator, the condition is unlikely to resolve due to the patient's underlying disease.
- e For all patients enrolled into Groups 3 to 7 blood samples will be collected on Day 1 at the following timepoints: Pre-dose, 0.25, 0.5, 1, 1.5, 2, 3, 4, 6, 8, 10, 12 hours after morning dosing and on day 8 and Day 15 at the following timepoints: Pre-dose and 1 hour after morning dosing.
- f For the additional patients that are recruited to Groups 3 onwards, blood samples will be collected on Day 29 at the following timepoints: pre-dose and post-dose between 0 - 0.5 hours, 0.5 to 1.5 hours, 1.5 - 3 hours, 3 - 6 hours, 6 - 8, and 8-12 hours.
- g For the additional patients that are recruited to Group 6 and 7, blood samples will be collected on Day 29 and Day 57 at the following timepoints: pre-dose and post-dose between 0 - 0.5 hours, 0.5 to 1.5 hours, 1.5 - 3 hours, 3 - 6 hours, 6 - 8, and 8-12 hours.
- h For the additional patients recruited to Group 6, 7 and 8, follow-up tumour assessments will be performed every 8 weeks (+/-1 week) until disease progression or study end (Tumour assessments for Group 8 patients should be stopped after Cycle 5). Any other sites at which new disease is suspected should also be appropriately imaged. If scans are performed outside of scheduled visit  $\pm$  1 week window interval and the patient has not progressed, every attempt should be made to perform the subsequent scans at their scheduled time points. Patients must be followed until progression regardless of whether study treatment is discontinued or delayed and/or protocol violation. A repeat scan is needed at the next scheduled tumour assessment (at least  $\geq$  4 weeks) for confirmation of a PR or CR by RECIST. Radiological examinations performed in the conduct of the study should be retained at site as source data and may be collected by the sponsor if required.
- i For the additional patients recruited to Group 6, 7 and 8, the imaging modalities used for RECIST assessment will be CT or MRI scans of chest, abdomen and pelvis for breast cancer and abdomen and pelvis for ovarian cancer with other regions as clinically indicated for the assessment of disease. An historical scan meeting the RECIST criteria as defined in Appendix F can be used for baseline assessment, but this must be performed no more than 28 days before the first dose of study medication.
- j After the follow up visit at the end of the 6th cycle of treatment (Visit 13), this visit should be repeated at least every 8 weeks until either the patient discontinues study treatment or the study is completed (clinical database is closed) (see Section 10.5).
- k Pre-menopausal women of child-bearing potential must have a negative urine or serum pregnancy test within 28 days prior to Day 1 and Day 1 (prior to treatment). In the event of suspected pregnancy during the study, the test should be repeated and, if positive, the patient discontinued from study treatment immediately.
- l Blood samples for CA-125 analysis should be taken prior to the morning dose of study medication for ovarian cancer patients only.
- m Haematology and clinical chemistry will also be performed on Day 43 and 71 for Group 3, 4 and 5 patients.
- n For the additional patients recruited to Group 6, 7 and 8, archival tumour samples will be requested. This is not mandatory and will not affect the enrolment of the patients into the study if not available. The sample can be collected at any time during the study.
- o For all patients enrolled into Group 8 blood samples will be collected at the following timepoints:

OD schedule

Day 1: pre-dose, 0.25, 0.5, 1, 1.5, 2, 3, 4, 6, 8, 10, 12, 24 hours after dosing

Day 8: pre-dose, 0.25, 0.5, 1, 1.5, 2, 3, 4, 6, 8, 10, 12, 24 hours after dosing

Day 57: pre-dose, 0 – 0.5, 0.5 – 1.5, 1.5 – 3, 3 – 6, 6 – 8, 8 – 12 hours after dosing

BD schedule:

Day 1: pre-dose, 0.25, 0.5, 1, 1.5, 2, 3, 4, 6, 8, 10, 12 hours after dosing

Day 8: pre-dose, 0 – 0.5, 0.5 – 1.5, 1.5 – 3, 3 – 6, 6 – 8, 8 – 12 hours after dosing

Day 57: pre-dose, 0 – 0.5, 0.5 – 1.5, 1.5 – 3, 3 – 6, 6 – 8, 8 – 12 hours after dosing

TDS schedule:

Day 1: pre-dose, 0.25, 0.5, 1, 1.5, 2, 3, 4, 6, 8 hours after dosing

Day 8: pre-dose, 0 – 0.5, 0.5 – 1.5, 1.5 – 3, 3 – 6, 6 – 8 hours after dosing

Day 57: pre-dose, 0 – 0.5, 0.5 – 1.5, 1.5 – 3, 3 – 6, 6 – 8 hours after dosing

p Questionnaire will be completed by site staff for any Group 8 patient spontaneously reporting or with an ongoing AE of nausea, vomiting or fatigue.

q For Group 8 patients these assessment should be stopped after Cycle 6.

r Urinalysis dipstick only performed post baseline where clinically indicated.

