- Tumour marker CA-125 will be assessed locally from blood samples taken at screening, visit 2 and every 8 weeks thereafter (applicable to ovarian cancer patients only). For Group 8 patients this assessment should stop at the end of cycle 5.
  - Tumour assessments (CT or MRI scans of chest, abdomen and pelvis for breast cancer and abdomen and pelvis for ovarian cancer with other regions as clinically indicated for the assessment of disease). For Group 8 patients this assessment should stop at the end of cycle 5.

[figure not shown]
Additional assessments for Groups 2, 3, 4, 5, 5.1.....6 and 7 include:

- Blood sampling for determination of AZD2281 plasma concentration at the following timepoints: Pre-dose, 0.25, 0.5, 1, 1.5, 2, 3, 4, 6, 8, 10, 12 hours after dosing at:
  - Group 2 – Day 8 and Day 15
  - Group 3 to 7 – Day 1
- Blood sampling for determination of AZD2281 plasma concentration at the following timepoints: Pre-dose and 1 hour after morning dose
  - Groups 3 to 7 – Day 8 and Day 15
- Blood sampling for determination of AZD2281 plasma concentration at the following timepoints: immediately prior to the first dose of the day and post the first dose of the day between 0 - 0.5 hours, 0.5 to 1.5 hours, 1.5 - 3 hours, 3 - 6 hours, 6 - 8 hours and 8 - 12 hours
  - Group 3 to 5 – Day 29
  - Group 6 and 7 – Day 29 and Day 57

Additional assessments for Group 8 include:

- Blood sampling for determination of AZD2281 plasma concentration for each dose schedule at the following timepoints:  
od schedule:
  - Day 1: pre-dose, 0.25, 0.5, 1, 1.5, 2, 3, 4, 6, 8, 10, 12, 24 hours after dosing
  - Day 8: pre-dose, 0.25, 0.5, 1, 1.5, 2, 3, 4, 6, 8, 10, 12, 24 hours after dosing
  - Day 57: pre-dose, 0 - 0.5, 0.5 - 1.5, 1.5 - 3, 3 - 6, 6 - 8, 8 - 12 hours after dosing

bd schedule:

- Day 1: pre-dose, 0.25, 0.5, 1, 1.5, 2, 3, 4, 6, 8, 10, 12 hours after dosing
- Day 8: pre-dose, 0 – 0.5, 0.5 – 1.5, 1.5 – 3, 3 – 6, 6 – 8, 8 – 12 hours after dosing
- Day 57: pre-dose, 0 – 0.5, 0.5 – 1.5, 1.5 – 3, 3 – 6, 6 – 8, 8 – 12 hours after dosing

tds schedule:

- Day 1: pre-dose, 0.25, 0.5, 1, 1.5, 2, 3, 4, 6, 8 hours after dosing
- Day 8: pre-dose, 0 – 0.5, 0.5 – 1.5, 1.5 – 3, 3 – 6, 6 – 8 hours after dosing
- Day 57: pre-dose, 0 – 0.5, 0.5 – 1.5, 1.5 – 3, 3 – 6, 6 – 8 hours after dosing

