#### 7.3.5.5 CT or MRI scans (RECIST)

The RECIST guidelines ([Therasse et al 2000](#)) for measurable, non-measurable, target and non-target lesions, and the objective tumour response criteria (complete response (CR), partial response (PR), Stable disease (SD) or progression of disease (PD)) are presented in [Appendix F](#). The RECIST criteria will be used to programmatically determine best overall response, PFS and duration of response. Patients with non-measurable disease only at baseline are excluded from Group 1 within the Continued supply phase expansion.

Baseline and follow-up contrast-enhanced CT scans of chest, abdomen and pelvis for breast cancer and abdomen and pelvis for ovarian cancer with other regions as clinically indicated for the assessment of disease. All baseline radiological tumour assessments must be performed no more than 28 days before the start of study treatment. Scans that were performed as part of standard of care prior to signature of the informed consent form can be analysed for the purposes of the study if they were performed within the correct time frame and of sufficient quality. Subsequent tumour assessments according to RECIST should be performed at the end of every 2 months (8 weeks +/-1 week) according to the planned study schedule (see [Table 6](#) and [Table 7](#)) up to objective progression by RECIST. Any other sites at which new disease is suspected should also be appropriately imaged. Patients must be followed until RECIST disease progression. (Group 8 only: RECIST assessments should stop after Cycle 5).

Radiological examinations performed in the conduct of the study should be retained at site as source data and may be collected by the sponsor if required.

All measurable lesions confirmed and assessed by radiological methods (CT or MRI scans) up to a maximum of 5 lesions per organ and 10 lesions in total, representative of all involved organs, should be identified as target lesions, recorded and measured at baseline, and at the time points specified in the protocol.

Non-target lesions will also be monitored throughout the study, and an overall assessment of response will be made; complete response, incomplete response/stable disease or progression. Details of any new lesions will also be recorded.

Tumour assessment will be performed in accordance with the protocol schedule until evidence of one of the following:

- Progression of disease by RECIST
- Death without evidence of progression

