### **12.3.3 Progression Free Survival**

PFS is defined as the time from randomisation to the earlier date of assessment of objective progression (per RECIST criteria) or death by any cause in the absence of progression. Patients without a progression event and still alive at the time of analysis will be censored at the time of their last evaluable objective tumour assessment. This includes patients who are lost to follow up or who withdraw consent.

If at any follow-up visit  $> 1/3$  of the target lesions recorded at baseline are missing then target lesion response will be not-evaluable (NE) (unless the sum of the longest diameters [LDs] of non-missing target lesion LDs would result in PD).

If  $\leq 1/3$  of lesions recorded at baseline are missing then the results will be scaled up (based on the baseline sizes) to give an estimated sum of diameters and this will be used in calculations.

A complete response will not be permissible at a visit response where there is missing data.

Objective progression is defined as at least a 20% increase in sum of longest diameters of the target lesions (compared to previous minimum sum) or an overall non-target lesion assessment of progression or a new lesion.

Patients are to have radiological scans until objective progression, regardless of whether they discontinue their randomised therapy or take another anti cancer therapy prior to progression.

Tumour assessments for Group 8 patients should be stopped after Cycle 5 (week 16). Dates of progression and death will be defined as follows:

- The actual date of progression will be used in the analysis regardless of whether the patient had previously discontinued all or part of their randomised therapy, started another anti cancer therapy, the event occurred between scheduled visits or previous

visits were not evaluable due to partially, or completely missing tumour assessments. This also applies to patients who die in the absence of progression.

- If radiological assessments take place on multiple dates at a visit then the date of progression used for analysis will be the earliest of target lesions or non-target lesion or new lesion dates, regardless of which component contributed to progression.

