#### **12.3.4 CA-125 response (GCIg criteria; [Rustin et al 2004](http://ctep.cancer.gov/resources/gcig/respdef_nov2005.doc); [http://ctep.cancer.gov/resources/gcig/respdef\\_nov2005.doc](http://ctep.cancer.gov/resources/gcig/respdef_nov2005.doc))**

Patients will be evaluable for CA-125 response if:

- Diagnosed with ovarian cancer
- a pre-treatment CA-125 level (taken within 2 weeks prior to starting treatment) is at least twice the upper limit of normal, and
- there is no more than a 10% fall in CA-125 between the two pre-treatment samples
- the same assay method is used for each sample from the same patient

A response according to CA-125 will be considered to have occurred if there is at least a 50% reduction in CA-125 levels from the last pre-treatment sample. The response must be confirmed and maintained for at least 28 days. The date when the CA-125 level is first reduced by 50% is the date of the CA-125 response.

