## **4. TUMOUR RESPONSE EVALUATION**

### **4.1 Schedule of evaluation**

All baseline tumour assessments must adequately assess tumour burden and should be performed no more than 28 days before the start of study treatment and ideally should be performed as close as possible to the start of study treatment. Any other sites at which new disease is suspected should also be adequately imaged at follow-up. Follow-up assessments will be performed every 8 weeks (+/- 1 week) after randomisation.

Bias in analysis can occur if one treatment group is examined more often or sooner than the other. If an unscheduled radiological and/or clinical tumour assessment is performed, and the patient has not progressed, the next scheduled tumour assessment should still be performed at the planned time (as detailed in the study plan). This schedule is to be followed in order to minimise any unintentional bias caused by some patients being assessed at a different frequency than other patients.

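### Table 7 puts follow-up scans and CA-125 samples on Days 57, 85 and (Groups 6 and 7 only) 141, but the text requires every 8 weeks; by the table, Group 8 would stop at week 12 instead of week 16

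*Protocol*

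**What the plan says.** Table 7 of the Protocol (Section 4.1.3) is the visit schedule for Groups 3-8. Its tumour-assessment row and its row "Blood sampling for CA-125" carry follow-up entries under visits 8 and 10 for Groups 6, 7 and 8, and under visit 12 for Groups 6 and 7 only. The header dates these visits Day 57, Day 85 and Day 141, each ±2 days.

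The text gives a different interval:

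- Table 7, footnote h: "follow-up tumour assessments will be performed every 8 weeks (+/-1 week) until disease progression or study end".
- Section 7.3.5.5: scans "at the end of every 2 months (8 weeks +/-1 week) according to the planned study schedule", with a reference to Tables 6 and 7.
- Appendix F, Section 4.1: "Follow-up assessments will be performed every 8 weeks (+/- 1 week) after randomisation".
- Section 7.2.2.3: CA-125 samples "taken at screening, visit 2 and every 8 weeks thereafter". Sections 7.3.5.6 and 8.1 give the same 8-week interval.

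On when Group 8 stops, Section 12.3.3 says "Tumour assessments for Group 8 patients should be stopped after Cycle 5 (week 16", closing the bracket there. Section 7.2.2.3 puts the stop at the end of cycle 5, and a cycle is 28 days.

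On confirmation, Section 12.3.4 says of CA-125: "The response must be confirmed and maintained for at least 28 days". For RECIST, Section 7.3.5.5 requires confirmation at the next scheduled assessment, no less than 4 weeks later. Appendix F, Section 5, expects that assessment at 8 weeks.

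**The concern.** No rule in the protocol produces a 4-week gap followed by an 8-week gap, yet Section 7.3.5.5 sends the reader to Table 7 as the planned schedule. A site could therefore follow the table in good faith and depart from the text.

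Three things would follow:

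- Group 8 would have its last scan and CA-125 sample at week 12. Patients without progression are censored at their last evaluable scan (Section 12.3.3), so PFS follow-up in that group would be cut directly.
- Groups 6 and 7 would have neither assessment marked at week 16 or week 24, and no mark at visit 13, which is the visit that repeats at least every 8 weeks.
- In Group 8 the only pair of post-baseline assessments available to confirm a response would sit exactly on the minimum permitted interval.

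Sites reading the text and sites reading the table would also date progression differently. Appendix F, Section 4.1, itself warns that unequal assessment timing can bias an analysis.

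**Working it through.** **Reading the table.** Both rows fill all 16 columns of the Table 7 header, so each entry can be counted to a visit. As a check on the alignment, other rows of the table land where their footnotes put them: ECG on Days 29 and 57 (footnote c), Group 3-5 haematology on Days 43 and 71 (footnote m), and PK on Days 1, 8, 15, 29 and 57 (footnotes e to g).

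**Days to weeks.** Week = (day − 1)/7. The 8-week rule gives day = 1 + 56k, for k = 1, 2, 3.

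| | First | Second | Third |
|---|---|---|---|
| Table 7 | Day 57 (week 8) | Day 85 (week 12) | Day 141 (week 20; Groups 6 and 7 only) |
| 8-week text | Day 57 (week 8) | Day 113 (week 16) | Day 169 (week 24; Groups 6 and 7 only) |

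The gaps are 28 and 56 days by the table, and 56 and 56 days by the text. Table 6, which applies the same 8-week rule to Group 1, marks Days 57, 113 and 169. Both tables mark every second visit from Day 57. Table 7 has extra columns for Days 43 and 71, so a carried-over pattern is a plausible cause, though that is an inference.

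**Group 8 end of assessment.** Table 7: Day 85, week 12. Section 12.3.3: week 16, which is Day 113. The shortfall is 16 − 12 = 4 weeks, or 4/16 = 25%. With 28-day cycles, week 16 is the end of cycle 4 (4 × 4 weeks) and cycle 5 ends at week 20 (Day 141), so the label in Section 12.3.3 does not fit itself. On the 8-week grid both limits still make Day 113 the last assessment: the next is Day 169, and even one week early (Day 162) it lies beyond Day 141.

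**Confirmation interval with the ±2-day visit window.** Interval = nominal gap + b − a, where a and b are the deviations of the first and second visits, each from −2 to +2.

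- Table 7, Day 57 to Day 85: 28 ± 4 = 24 to 32 days.
- 8-week text, Day 57 to Day 113: 56 ± 4 = 52 to 60 days.

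For the 28-day gap the interval falls short only when b < a. With independent deviations from the same symmetric distribution, P(b < a) = (1 − P(a = b))/2. The documents do not say how visits fall within the window, so a range is shown:

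| Assumed visit dates | P(a = b) | P(interval < 28 days) |
|---|---|---|
| All on the nominal day | 1 | 0% |
| 80% on the nominal day, rest spread evenly | 0.64 + 4 × 0.05² = 0.65 | 17.5% |
| 50% on the nominal day, rest spread evenly | 0.25 + 4 × 0.125² = 0.3125 | 34% |
| Triangular (weights 1, 2, 3, 2, 1) | 19/81 | 38% |
| Uniform over five days | 1/5 | 40% (10 of 25 combinations) |

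On the 8-week schedule the probability is 0% in every row. Even with the ±1-week scan window at both ends, that gap is 56 ± 14 = 42 to 70 days.

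**The case against.** **Confirmation failure.** A reader might infer that the 28-day rule would often fail. The documents do not support that. At nominal dates the interval is 28 days, which satisfies both confirmation rules. A shortfall requires a site to follow the table over the text and the second visit to drift earlier relative to the first. No frequency is given for either.

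**Scan windows.** Putting the ±1-week window on both Day 57 and Day 85 gives 14 to 42 days and 105 of 225 combinations (47%) below 28 days. That mixes two schedules: footnote h attaches its ±1 week to an 8-week interval, so a site using that interval would not be scanning on Day 85. The figure should not be used.

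**Groups 6 and 7.** The missing scan mark at visit 13 might be taken to mean that scanning stops. It does not, because footnote h requires 8-weekly scans until progression or study end. For CA-125, the Day 141 sample could still show that a response was maintained.

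**Group 8 stop.** Three different end points might seem to be stated. In effect there are two: week 16 and the end of cycle 5 both give Day 113 on the 8-week grid, and only Day 85 differs.

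**Importance.** The primary objective is safety, PFS is a descriptive Kaplan-Meier summary, and the tumour-size comparison in Section 12.4.5 is at eight weeks, where table and text agree. Nothing ties a site's reading to treatment arm. All of this stands and limits the size of the point.

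**Extraction.** Some superscripts in the table appear garbled, so a look at the original page is sensible. The agreement of three other rows with their footnotes makes a column shift unlikely.

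None of this explains the Day 85 and Day 141 cells, which still contradict their own footnote.

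**Conclusion.** The inconsistency is real. Two Table 7 rows contradict footnote h, Sections 7.2.2.3, 7.3.5.5, 7.3.5.6 and 8.1, and Appendix F. A site following the table would end Group 8 scans and CA-125 sampling at week 12 instead of week 16, a quarter earlier. It would also leave that group a single confirmation pair with no margin: nominally compliant, 24 to 32 days apart within the visit windows, and short of 28 days in 0 to 40% of CA-125 pairs. That range rests on independent visit deviations and the assumed date distributions; the documents supply no rate. The 8-week schedule removes the risk.

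The consequence is confined to secondary, descriptive efficacy outcomes (PFS, best overall response, CA-125 response) and falls mainly on Group 8. For RECIST, which ties confirmation to the next scheduled scan, the short gap would also touch Groups 6 and 7. The point deserves correction but does not threaten the primary safety objective.

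**What to change.** Reconcile both Table 7 rows with the 8-week rule: follow-up entries at visit 8 (Day 57) and visit 11 (Day 113) for Groups 6, 7 and 8, and at visit 13 (Day 169) and its 8-weekly repeats for Groups 6 and 7 only. Remove the entries at visits 10 and 12.

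State Group 8's last assessment once, by day or week, and use it in footnote h and in Sections 7.2.2.3, 7.3.5.5, 7.3.5.6, 8.1 and 12.3.3. Day 113 (week 16) fits both the 8-week rule and the week named in Section 12.3.3. The cycle label then needs correcting, since week 16 closes cycle 4.

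The cost is a table and wording correction in an amendment, with no assessments beyond those the text already requires. One limit remains: a Group 8 response first seen at the last assessment has no later assessment to confirm it under either schedule.
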